### 9.4.4 Sensitivity analyses

The two primary efficacy variables will be analyzed at each time point for the Full Analysis Set using a logistic regression model with treatment and body weight (<90 kg,  $\geq$ 90 kg) as explanatory variables (Stokes, Davis, and Koch, 2012). The odds ratios and 95% confidence intervals for the odds ratios based on the fitted model will be reported.

Estimates of differences between the two proportions within each stratum will be calculated and examined for meaningful treatment-by-stratum interaction.

## 9.5 Analysis of secondary variables

### 9.5.1 Efficacy variables

The secondary efficacy objective (i.e., explore the modulation of subcutaneous adipose tissue and skin inflammation from baseline to Week 52) will be assessed using the same two primary efficacy variables, but measured at Week 52.

### 9.5.2 Safety variables

[figure not shown]
The assessment of safety will be based mainly on the frequency of adverse events and laboratory data. Other safety data, including vital signs (blood pressure, weight, waist circumference, BMI), and clinical laboratory variables (glucose, insulin, hs-CRP, HOMA-IR, HbA1c) will be summarized by stratum, as appropriate.

Adverse events will be summarized by presenting, for each treatment group, the number and percentage of patients having any adverse event, having an adverse event in each body system and having each individual adverse event. Any other information collected (e.g., severity or relatedness to study medication) will be listed, as appropriate.

Adverse events and serious adverse events up to and including Week 12 visit will be included in the database for the analysis at the primary analysis time point (Week 12). All Adverse events and serious adverse events will be included in the final database analysis (Week 53).

Laboratory variables and other safety variables will be summarized, as appropriate.

Analysis of safety data will be based on the Safety Set.

Confidential

# 9.7 Interim analyses

The database of this study will be locked twice, first after the end of double-blind treatment period (Week 12) and again at the end of the follow-up period (Week 53). Data analyses will follow each database lock. The main analysis for the primary objective will be done at Week 12. As Week 12 analysis considered primary and no specific hypothesis is pre-identified for testing, adjustment of significance level due to this interim analysis is irrelevant.

In addition, after all patients complete their baseline visit, the demographic and baseline characteristics may be summarized to help design new studies.

Table 9-1

## 9.8 Sample size calculation

The table below considers total sample sizes of 75 patients (50 in secukinumab group and 25 in placebo group) and 99 patients (66 in secukinumab group and 33 in placebo group) to estimate the difference between the two groups with respect to the pooled estimate of the two percentages of patients who have the "event" at Week 12 for each of the two primary efficacy variables. The entries in the table are the "margin of error" (half-width of confidence interval) for a two-sided 95% confidence interval (Julious and Patterson, 2004; Kianifard and Islam, 2011; nQuery Advisor 7.0).

Sample size calculations for percentage of patients who have the

Confidential

"event"				
Percentage with "event"	Half-width of confidence interval for $n = 75$	Half-width of confidence interval for $n = 99$		
30%	25.0%	21.4%		
40%	26.5%	22.7%		
50%	27.0%	23.2%		
60%	26.5%	22.7%		
70%	25.0%	21.4%		

Based on the results in the above table, it was decided that approximately 75 randomized patients (50 in secukinumab group and 25 in placebo group) will be randomized in this exploratory study to estimate the difference in response rates between the two treatment groups.

# 10 Ethical considerations

## 10.1 Regulatory and ethical compliance

This clinical study was designed and shall be implemented, executed and reported in accordance with the ICH Harmonized Tripartite Guidelines for Good Clinical Practice, with applicable local regulations (including European Directive 2001/20/EC, US CFR 21, and Japanese Ministry of Health, Labor, and Welfare), and with the ethical principles laid down in the Declaration of Helsinki.

## 10.2 Informed consent procedures

Eligible patients may only be included in the study after providing written (witnessed, where required by law or regulation), IRB/IEC-approved informed consent, or, if applicable after such consent has been provided by a legally acceptable representative(s) of the patient. In cases where the patient's representative gives consent, the patient must be informed about the study to the extent possible given his/her understanding. If the patient is capable of doing so, he/she must indicate assent by personally signing and dating the written informed consent document or a separate assent form. Informed consent must be obtained before conducting any study-specific procedures (e.g., all of the procedures described in the protocol). The process of obtaining informed consent must be documented in the patient's source documents.

Novartis will provide to investigators in a separate document a proposed informed consent form that complies with the ICH GCP guideline and regulatory requirements and is considered appropriate for this study. Any changes to the proposed consent form suggested by the investigator must be agreed to by Novartis before submission to the IRB/IEC, and a copy of the approved version must be provided to the Novartis or CRO monitor after IRB/IEC approval.

# 10.3 Responsibilities of the investigator and IRB/IEC

Before initiating a trial, the investigator/institution must obtain approval/favorable opinion from the Institutional Review Board/Independent Ethics Committee (IRB/IEC) for the trial protocol, written informed consent form, consent form updates, patient recruitment procedures (e.g., advertisements) and any other written information to be provided to patients. Prior to study start, the investigator is required to sign a protocol signature page confirming his/her agreement to conduct the study in accordance with these documents and all of the instructions and procedures found in this protocol and to give access to all relevant data and records to Novartis monitors, auditors, Novartis Quality Assurance representatives, designated agents of Novartis, IRBs/IECs, and regulatory authorities as required. If an inspection of the clinical site is requested by a regulatory authority, the investigator must inform Novartis immediately that this request has been made.

# **10.4** Publication of study protocol and results

The key design elements of this protocol will be posted in a publicly accessible database such as clinicaltrials.gov. In addition, upon study completion and finalization of the study report the results of this trial will be either submitted for publication and/or posted in a publicly accessible database of clinical trial results.

# 10.5 Quality Control and Quality Assurance

Novartis maintains a robust Quality Management (QM) system that includes all activities involved in quality assurance and quality control, including the assignment of roles and responsibilities, the reporting of results, and the documentation of actions and escalation of issues identified during the review of quality metrics, incidents, audits and inspections.

Audits of investigator sites, vendors, and Novartis systems are performed by Novartis Pharma Auditing and Compliance Quality Assurance, a group independent from those involved in conducting, monitoring or performing quality control of the clinical trial. The clinical audit process uses a knowledge/risk based approach.

Audits are conducted to assess GCP compliance with global and local regulatory requirements, protocols and internal SOPs, and are performed according to written Novartis processes.

# 11 Protocol adherence

This protocol defines the study objectives, the study procedures and the data to be collected on study participants. Additional assessments required to ensure safety of patients should be administered as deemed necessary on a case by case basis. Under no circumstances is an investigator allowed to collect additional data or conduct any additional procedures for any research-related purpose involving any investigational drugs under the protocol.

Investigators ascertain they will apply due diligence to avoid protocol deviations. If an investigator feels a protocol deviation would improve the conduct of the study this must be considered a protocol amendment, and unless such an amendment is agreed upon by Novartis and approved by the IRB/IEC and health authorities, where required, it cannot be implemented.

# **11.1 Protocol amendments**

Any change or addition to the protocol can only be made in a written protocol amendment that must be approved by Novartis, health authorities where required, and the IRB/IEC prior to implementation. Only amendments that are intended to eliminate an apparent immediate hazard to patients may be implemented immediately provided the health authorities are subsequently notified by protocol amendment and the reviewing IRB/IEC is notified. Notwithstanding the need for approval of formal protocol amendments, the investigator is expected to take any immediate action required for the safety of any patient included in this study, even if this action represents a deviation from the protocol. In such cases, the reporting requirements identified in Section 7 Safety Monitoring must be followed.

# 13 Appendix 1: Clinically notable laboratory values and vital signs

The following criteria will be used to define expanded limits and notable abnormalities of key laboratory tests. Notable values for blood pressure and pulse are presented in Section 6.7.2.

No specific action is pre-defined within this protocol to respond to specific notable laboratory or vital signs values. It will be decided by the investigator/qualified site staff whether and which specific action needs to be taken to respond to any notable values, taking into account the overall status of the patient.

#### Liver function and related variables

ALT (SGPT) AST (SGOT) Total bilirubin Alkaline phosphatase	> 3 x Upper Limit of Normal (ULN) > 3 x ULN > 1.5 x ULN > 2 x ULN
Renal function	
Creatinine (serum)	> 1.5 x ULN
Hematology variables	
Hemoglobin	≥ 2.0 g/dL decrease from baseline
Platelet count	< Lower Limit of Normal (LLN)
White blood cell	< 0.8 x LLN
Neutrophils	< 0.9 x LLN
Eosinophils	> 1.1 x ULN
Lymphocytes:	> 1.1 x ULN

#### **Appendix 2: Tuberculosis screening flowchart** 14

The subject will not be eligible for randomization if "active tuberculosis is present "or if "latent tuberculosis is present and is untreated as per local guidelines." \*If the first QuantiFERON® TB-Gold In-Tube test (QFT) is indeterminate, the investigator may choose to perform a second

QFT or refer the subject for tuberculosis workup per local guidelines.

\*" If the result of any QFT is "positive" or the results of 2 sequential QFTs are "indeterminate", the subject must be referred to have a tuberculosis workup per local guidelines (if no workup within 12 weeks prior to randomization is available).

# 16 Appendix 4: Psoriasis Area and Severity Index (PASI) and Body Surface Area (BSA)

Body Region	Erythema (E)	Thickening (I) (plaque elevation, induration)	Scaling (D) (desquamation)	True Area % (covered by lesions)
Head and Neck (H)	None (0)     Slight (1)     Moderate (2)     Severe (3)     Very severe (4)	None (0)     Slight (1)     Moderate (2)     Severe (3)     Very severe (4)	None (0)     Slight (1)     Moderate (2)     Severe (3)     Very severe (4)	Record % (0-100)
Trunk, Axillae and Groin (T)	None (0)     Slight (1)     Moderate (2)     Severe (3)     Very severe (4)	None (0)     Slight (1)     Moderate (2)     Severe (3)     Very severe (4)	None (0)     Slight (1)     Moderate (2)     Severe (3)     Very severe (4)	Record % (0-100)
Upper Limbs (U)	None (0)     Slight (1)     Moderate (2)     Severe (3)     Very severe (4)	None (0)     Slight (1)     Moderate (2)     Severe (3)     Very severe (4)	None (0) Slight (1) Moderate (2) Severe (3) Very severe (4)	Record % (0-100)
Lower Limbs and Buttocks (L)	None (0)     Slight (1)     Moderate (2)     Severe (3)     Very severe (4)	None (0)     Slight (1)     Moderate (2)     Severe (3)     Very severe (4)	None (0) Slight (1) Moderate (2) Severe (3) Very severe (4)	Record % (0-100)

# 17 Appendix 5: Sample Log Table

Sample log time schedule for sampling for adipose tissue,

#### Novartis Amended Protocol Version 02 (Clean)

#### Confidential

Week	Visit No.	Time Point	Blood - Microparticles & Leukocytes (FACS - ambient)	Blood - Microparticles & Leukocytes (FACS - ambient)	Blood - Microparticles & Leukocytes (FACS - frozen)	Blood - Microparticles & Leukocytes (FACS - frozen) Sample #
Screening	1	Weeks -4 to Baseline				
Baseline	2	predose	10 mL	601	10 mL	605
Week 1 (Day 8)	3					
Week 2 (Day 15)	4					
Week 3 (Day 22)	5					
Week 4 (Day 29)	6	predose				
Week 8 (Day 57)	7					
Week 12 (Day 85)	8	predose	10 mL	602	10 mL	606
Week 13 (Day 92)	9					
Week 16 (Day 113)	10					
Week 24 (Day 169)	11	predose	10 mL	603	10 mL	607
Week 32 (Day 225)	12					
Week 40 (Day 281)	13					
Week 48 (Day 337)	14					
Week 52 (Day 365)	15		10 mL	604	10 mL	608
Week 53 (Day 372)						
Total mL:			40		40	
Consolidated total mL:	147.5					

Novartis Amended Protocol Version 02 (Clean) Confidential


TB Tuberculosis

TNF tumor necrosis factor

Introduction

This statistical analysis plan (SAP) describes the statistical methodologies which will be used in the phase IV clinical trial (CAIN457AUS07). This is an exploratory, randomized, double-blind, placebo-controlled, parallel-group, multicenter study in patients with moderate to severe plaque psoriasis patients.

[figure not shown]
The purpose of this study is to explore changes in subcutaneous adipose tissue and skin inflammation in patients with moderate to severe plaque psoriasis treated with secukinumab 300mg compared to placebo at Week 12.

1.1 Study design

This study uses a randomized, double-blind, placebo-controlled, parallel-group, multicenter design. The study consists of five periods:

- Screening (from 1-4 weeks before randomization);
- Double-blind Treatment Period (Randomization to Week12 pre-dose);
- Double-blind Induction Period (Week 12 post dose to Week 15 dose);
- Open-label Treatment Period (Week 16 to Week 52); and
- Follow-up Period (1 week).

A schematic of the study design is presented below:

Approximately 75 moderate to severe plaque psoriasis patients (50 in secukinumab group and 25 in placebo group) from approximately 15 sites will be randomized at Visit 2/Baseline in a 2:1 ratio

to receive secukinumab 300 mg or placebo, respectively. Randomization will be stratified by body weight collected at Visit 2 (<90 kg or ≥90 kg).

An interim analysis is planned after Week 12, which is the primary analysis time point for the study. Interim analysis will be performed after all patients have completed the Week 12 visit and the database is locked.

1.2 Study objectives and endpoints

Table 1.1 Objectives and related endpoints

Objective(s)	Endpoint(s)	
Primary Objective(s)	Endpoint(s) for primary objective(s)	
To explore the modulation of subcutaneous adipose tissue and skin inflammation from baseline to Week 12 in patients with moderate to severe plaque psoriasis treated with secukinumab compared to placebo	Response of psoriasis skin lesions to treatment as measured by: a) Response in skin histology/K16 expression to treatment (yes, no) b) PASI 90 (yes, no)	
Secondary Objective(s)	Endpoint(s) for secondary objective(s)	
To explore changes in biometric measurements from baseline to Week 12 in patients with moderate to severe plaque psoriasis treated with secukinumab compared to placebo	Vital signs (blood pressure, weight, waist circumference, BMI), clinical laboratory variables (glucose, insulin, hs-CRP, HOMA-IR, HbA1c)	
To explore the modulation of subcutaneous adipose tissue and skin inflammation from baseline to Week 52 in patients with moderate to severe plaque psoriasis treated with secukinumab	Response of psoriasis skin lesions to treatment as measured by: a) Response in skin histology/K16 expression to treatment (yes, no) b) PASI 90 (yes, no)	

2 Statistical methods

2.1 Data analysis general information

Novartis will perform the statistical analysis.

Data will be analyzed by the statistical software SAS, Version 9.4 according to Section 9 (Data Analysis) of the study protocol which will also be available in Appendix 16.1.1 of the Clinical Study Report (CSR). Important information is given in the following sections and details are provided, as applicable, which will also be in Appendix 16.1.9 of the CSR.

Data up to Week 12 will be presented for the Week 12 interim analysis and all data will be presented for final analysis.

It is planned that the data from all centers that participate in this protocol will be combined, so that an adequate number of patients will be available for analysis.

Summary statistics for continuous variables will include n, mean, standard deviation, standard error of the mean, minimum, lower quartile, median, upper quartile, interquartile range, and maximum.

Summary statistics for discrete variables will be presented in contingency tables and will include frequencies and percentages.

Primary efficacy variables will be summarized for lesional samples.

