## 5.4 Treatment blinding

Patients, investigators/site staff, persons performing assessments, and Novartis study personnel will remain blinded to individual treatment assignment from the time of randomization until the final database lock at Week 53, using the following methods:

Confidential

- 1. Randomization data will be kept strictly confidential until the time of unblinding, and will not be accessible by anyone else involved in the study with the following exceptions:
  - specific vendors whose role in trial conduct requires their unblinding (e.g., IRT)
  - Drug Supply Management (DSM);
- 2. The identity of secukinumab and placebo prefilled syringes (PFS) will be concealed by identical packaging, labeling, schedule of administration, and appearance.

At the Week 12 primary analysis time point, there will be a database lock after all patients have completed the Week 12 visit. At that time, only the statistician and programmer(s) from the designated CRO will be unblinded in order to perform the analysis. Results from the analyses of all data through Week 12, including the data for the primary efficacy variable, will be reported. For publication purposes, summary results from the Week 12 primary analysis time point may be shared with the health care community, however individual patient-level data will remain blinded until the end of the trial.

Unblinding will only occur in the case of patient emergencies (see Section 5.5.9), at the time of the primary analysis (Week 12) for designated CRO personnel only, and at the conclusion of the study.

A full analysis of all data collected up to Week 53 will be performed when all patients have completed Follow-up Visit 1/Week 53.

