# 9 Data analysis

A designated Contract Research Organization will perform the statistical analysis.

It is planned that the data from all centers that participate in this protocol will be combined, so that an adequate number of patients will be available for analysis.

The analysis will be conducted on all patient data at the end of Week 12 and at the time the trial ends at Week 53. Any data analysis carried out independently by the investigator should be submitted to Novartis before publication or presentation.

Efficacy, safety, and other data will be summarized for all weeks up to Week 53. For continuous variables, summary statistics (mean, standard deviation, median, 25th and 75th percentiles, interquartile range, minimum, and maximum) at each time point and for change

from baseline to each time point will be reported by treatment group. For discrete variables, frequency counts and percentages at each time point will be reported by treatment group.

Confidential

Primary efficacy variables will be summarized for lesional samples.

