2.3.1 Patient disposition

The number of patients screened will be presented along with the reasons for screen failures for all patients as specified in the screening phase disposition eCRF.

The number and percentage of patients in the randomized set (RAN) who, completed study periods (double-blind treatment period and open-label treatment period) and who discontinued the study prematurely including the reason for discontinuation will be presented for each treatment group and all patients.

Patients withdrawing consent will be listed with reason for withdrawal.

The number and percentage of patients with protocol deviations will be tabulated by treatment groups and listed separately by treatment groups.

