The investigator is responsible for collecting the components or scoring signs and total regional area for all visits. PASI and total BSA calculations will be done by investigator at screening and randomization only; The PASI scores after randomization will be calculated by Novartis and will be used in the analysis and for derivation of PASI response values (see below).

Table 2-5 The PASI scoring system

I able 2-3	The FASI scoring system				
Body region	Erythema (E)	Thickening (plaque elevation, induration, I)	Scaling (desquamation, D)	Area score (based on true area %, A)*	
Head (H) [†]	0=none 1=slight 2=moderate 3=severe 4=very severe	0=none 1=slight 2=moderate 3=severe 4=very severe	0=none 1=slight 2=moderate 3=severe 4=very severe	0 = no involvement 1 = >0-<10% 2 = 10-<30% 3 = 30-<50% 4 = 50-<70% 5 = 70-<90% 6 = 90-100%	
Trunk (T)‡	0=none 1=slight 2=moderate 3=severe 4=very severe	0=none 1=slight 2=moderate 3=severe 4=very severe	0=none 1=slight 2=moderate 3=severe 4=very severe	0 = no involvement 1 = >0-<10% 2 = 10-<30% 3 = 30-<50% 4 = 50-<70% 5 = 70-<90% 6 = 90-100%	
Upper limbs (U)	0=none 1=slight 2=moderate 3=severe 4=very severe	0=none 1=slight 2=moderate 3=severe 4=very severe	0=none 1=slight 2=moderate 3=severe 4=very severe	0 = no involvement 1 = >0-<10% 2 = 10-<30% 3 = 30-<50% 4 = 50-<70% 5 = 70-<90% 6 = 90-100%	
Lower limbs (L)§	0=none 1=slight 2=moderate 3=severe 4=very severe	0=none 1=slight 2=moderate 3=severe 4=very severe	0=none 1=slight 2=moderate 3=severe 4=very severe	0 = no involvement 1 = >0-<10% 2 = 10-<30% 3 = 30-<50% 4 = 50-<70% 5 = 70-<90% 6 = 90-100%	

^{*} Percentage (not score) of body region (not whole body) affected will be entered in the eCRF.

[†] Neck is assessed as part of the Head (H) body region.

- [‡] Axillae and groin are assessed as part of the Trunk (T) body region.
- § Buttocks are assessed as part of the Lower limbs (L) body region.

The following definitions are possible efficacy evaluations that can be used in clinical trials in psoriasis:

• PASI 90 response: patients achieving ≥ 90% improvement (reduction) in PASI score compared to baseline are defined as PASI 90 responders

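### SAP 2.1 gives the analysis, Week 12 included, to Novartis, while the protocol gives it to a CRO and unblinds only CRO staff before the Week 53 lock

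*SAP*

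**What the plan says.** On who performs the analysis, the two documents differ.

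- SAP 2.1: "Novartis will perform the statistical analysis". No lock or time point is excepted. The same section goes on to describe what is presented at the Week 12 interim analysis and at the final analysis, and SAP 2.14 has analyses following each of two database locks.
- Protocol Section 9: "A designated Contract Research Organization will perform the statistical analysis".

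On who may know the treatment assignment, protocol 5.4 is specific.

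- Until the end: "Novartis study personnel will remain blinded to individual treatment assignment from the time of randomization until the final database lock at Week 53".
- At the Week 12 lock: "At that time, only the statistician and programmer(s) from the designated CRO will be unblinded in order to perform the analysis". The section repeats this restriction when it lists the occasions for unblinding.
- Summary Week 12 results may be shared for publication, but "individual patient-level data will remain blinded until the end of the trial".
- The standing exceptions are vendors whose role requires unblinding, such as the IRT provider, and Drug Supply Management. Emergency code breaks are handled separately.

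The SAP describes no unblinded or firewalled Novartis team. Its Section 4, on changes from the protocol-specified analyses, reads as not applicable. On outputs, SAP 2.3.1 says that protocol deviations "will be tabulated by treatment groups and listed separately by treatment groups", and does not say at which lock the listing is produced.

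**The concern.** The blind that protocol 5.4 promises from Week 12 to Week 53 rests on one arrangement: an outside CRO holds the codes and the sponsor's study staff do not. SAP 2.1 removes that arrangement in one sentence and puts nothing in its place. A programmer or statistician working from the SAP would expect Novartis to receive the codes at the Week 12 lock. One working from the protocol would expect the opposite.

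What is at stake is the integrity of the stated blind, and what the study report can say about it. After the Week 12 lock the trial is still collecting, querying and deriving data up to Week 53. The original arm still matters in reporting, because SAP 2.3 and 2.8 present later periods as secukinumab versus placebo/secukinumab. Some handling decisions also remain open: protocol 8.3 has deviations determined before the codes are released, and SAP 2.8.1 allows the threshold for common adverse events to be revised after the dry run. Making such decisions without knowledge of arm is what the protocol's arrangement protects.

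**Working it through.** No figure in the plan bears on this point, so the check is a comparison of the texts, followed by a count that bounds its reach.

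**Step 1: does the SAP sentence cover Week 12?** Yes. SAP 2.1 is the general section for all analyses and itself refers to the Week 12 interim analysis. SAP 1.1 and 2.14 place that analysis after the Week 12 lock. Nothing limits the Novartis role to the final analysis.

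**Step 2: does the Week 12 analysis need treatment codes?** Yes. SAP 2.5.2 requires the difference between secukinumab and placebo in the percentage of patients with each outcome, with a 95% confidence interval. This cannot be computed without each patient's arm.

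**Step 3: does the protocol allow Novartis to hold the codes then?** No. Protocol 5.4 says that "only the statistician and programmer(s) from the designated CRO will be unblinded in order to perform the analysis". An analyst on the Novartis study team is also barred by the rule on study personnel. A Novartis analyst outside the study team might fall outside that rule, but would still not be CRO staff.

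**Step 4: is the difference declared?** No. SAP Section 4 records no change. SAP 2.1 also says the data are analysed according to protocol Section 9, which is the section that names the CRO. The SAP therefore both points to the protocol and departs from it.

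**Step 5: how much data could lie after the lock?** In protocol Table 6-1 the post-baseline PASI assessments are at Weeks 4, 8, 12, 16, 24, 32, 40, 48 and 52, which makes 9. Those after Week 12 are at Weeks 16, 24, 32, 40, 48 and 52, so 6 of 9. The Week 52 biopsy also follows. Follow-up after the Week 12 visit is at most 53 − 12 = 41 weeks.

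These are ceilings for a single patient. The lock comes only after all patients have completed Week 12, so patients who enrolled earlier would already have later visits recorded. The documents give no enrolment timetable from which to estimate the share of data actually exposed.

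**The case against.** The strongest reply is that SAP 2.1 is a general statement of responsibility. It does not say who holds the codes at Week 12, it refers back to protocol Section 9, and the SAP nowhere relaxes protocol 5.4. On that reading the defect is unclear responsibility and not a planned breach. It stands to this extent: nothing shows an intention to unblind the study team. It does not remove the conflict, because whoever performs the Week 12 comparison must hold the codes, and the SAP names Novartis for that task.

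A reader might infer three stronger things that the documents do not support.

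- **That the SAP plans to release patient-level listings by arm to Novartis at Week 12.** Only the protocol-deviation listing is expressly split by treatment group; the layout of the others is not stated. An unblinded CRO programmer could produce that listing without breaching protocol 5.4, and the SAP's silence on timing is not a contradiction.
- **That the people who review and query eCRF data would know each patient's arm.** Protocol 8.3 lets Novartis staff or a CRO acting for Novartis do this review, and nothing says that reviewers receive codes or are the same people as the analysts.
- **That the Week 52 PASI 90 result would be biased because "The PASI scores after randomization will be calculated by Novartis".** The score is a fixed formula applied to components scored by the investigator or a trained designee, who stays blinded to the original assignment. Knowing the arm cannot change that arithmetic.

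It is also fair to say that the consequences are limited. The Week 52 efficacy analysis presents percentages (SAP 2.7.2), and no formal hypothesis is tested (SAP 5.4.1).

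**Conclusion.** The conflict is real and lies in the current text of both documents. Followed as written, the SAP would unblind Novartis at the Week 12 lock, against protocol 5.4, without a firewalled team and without a declared change. For data handled after that lock, the report could not then claim the blinding that the protocol describes. The breach of the stated rule would apply to the whole randomised population of about 75 patients.

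The effect on results is likely to be small. The Week 12 primary result is untouched: its assessments precede the Week 12 dose, and the data are locked before any analyst is unblinded. After Week 12 all patients receive secukinumab, and site staff and assessors remain blinded to the original assignment. The ceilings of 6 of 9 PASI visits and 41 weeks of follow-up bound what could lie after the lock; they do not measure bias.

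The conclusion assumes that the SAP sentence means what it says and that no separate document, outside those reviewed, sets up an unblinded team. It should be corrected because the protection is already planned and restoring it costs almost nothing.

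**What to change.** Add two statements to SAP 2.1:

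1. The designated CRO performs the Week 12 analysis, and Novartis receives only aggregate results until the Week 53 lock.
2. Any patient-level output that shows treatment group, such as the protocol-deviation listing in SAP 2.3.1, is not released outside the unblinded CRO team before that lock.

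This uses the CRO role already in the protocol. It changes no estimate, sample size or visit, and needs no protocol amendment.

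If Novartis is to do the Week 12 analysis, the cost is higher. Name a firewalled team separate from the study personnel, amend protocol 5.4 and Section 9 to match, and record the change in SAP Section 4. Section 4 may be meant for changes to the analyses themselves, but it is where a reader will look for a departure from the protocol.
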